8.2.5. Guidance for Venous Thromboembolic Events

In breast cancer, VTE has been identified as an adverse drug reaction (ADR) for abemaciclib in combination with ET. In the randomized Phase 3 studies in participants with breast cancer who received abemaciclib in combination with ET, a greater number of participants experienced VTEs in the abemaciclib plus ET arms than in the placebo plus ET arm or ET alone arm. The majority of participants who experienced VTEs were treated with anticoagulants. In studies with single-agent abemaciclib use in the metastatic breast cancer population or other tumor types, including non-small cell lung cancer, no increased rates of VTEs were treated with other anticancer agents. At this time, the mechanism underlying the association between abemaciclib and the occurrence of VTEs is not known.

Monitor participants for signs and symptoms of deep vein thrombosis and pulmonary embolism and treat as medically appropriate. Refer to Section 6.6.3 for guidance on dose adjustments of abemaciclib for patients with VTEs.

8.2.6. Guidance for Interstitial Lung Disease/Pneumonitis

Interstitial lung disease (ILD)/pneumonitis has been identified as an ADR for abemaciclib. The majority of events observed in clinical trials were Grade 1 or Grade 2 with serious cases and fatal events reported. Additional information is available in the IB.

Ask participants to report any new or worsening pulmonary symptoms, such as dyspnea, cough, and fever, and investigate and treat as per local clinical practice (including corticosteroids as appropriate). If ILD/pneumonitis is suspected, investigations may include imaging, such as high-resolution CT, bronchoalveolar lavage, and biopsy as clinically indicated. Refer to Section 6.6.3 for guidance on dose adjustments or discontinuation of abemaciclib for patients with ILD/pneumonitis.

8.3. Adverse Events, Serious Adverse Events, and Product Complaints

Investigators are responsible for monitoring the safety of participants who have entered this study and for alerting the Sponsor or its designee to any event that seems unusual, even if this event may be considered an unanticipated benefit to the participant.

The investigator is responsible for the appropriate medical care of participants during the study.

Investigators must document their review of each laboratory safety report.

The investigator remains responsible for following, through an appropriate health care option, AEs that are serious or otherwise medically important, considered related to the investigational product or the study, or that caused the participant to discontinue the investigational product before completing the study. The participant should be followed until the event resolves, stabilizes with appropriate diagnostic evaluation, or is otherwise explained. The frequency of follow-up evaluations of the AE is left to the discretion of the investigator.

Lack of drug effect is not an AE in clinical studies, because the purpose of the clinical study is to establish treatment effect.

After the ICF is signed, study site personnel will record via CRF the occurrence and nature of each participant's preexisting conditions, including clinically significant signs and symptoms of the disease under treatment in the study. In addition, site personnel will record any change in the condition(s) and any new conditions as AEs. Investigators should record their assessment of the potential relatedness of each AE to protocol procedure, investigational product, via CRF.

The investigator will interpret and document whether or not an AE has a reasonable possibility of being related to study treatment, study device, or a study procedure, taking into account the disease, concomitant treatment, or pathologies.

A "reasonable possibility" means that there is a cause and effect relationship between the investigational product, study device, and/or study procedure and the AE.

The investigator answers yes/no when making this assessment.

Planned surgeries and nonsurgical interventions should not be reported as AEs unless the underlying medical condition has worsened during the course of the study.

Abnormal laboratory values should ONLY be reported as an AE if they are clinically relevant (See Section 10.6, Appendix 6).

If a participant's investigational product is discontinued as a result of an AE, study site personnel must report this to the Sponsor or its designee via CRF, clarifying if possible the circumstances leading to any dosage modifications, or discontinuations of treatment.

The definitions of the following events can be found in Section 10.6, Appendix 6:

- Adverse events
- Serious adverse events, and
- Product complaints.

These events will be reported by the participant (or, when appropriate, by a caregiver, surrogate, or the participant's legally authorized representative).

The investigator and any qualified designees are responsible for detecting, documenting, and recording events that meet these definitions and remain responsible for following up events that are serious, considered related to the study intervention or study procedures, or that caused the participant to discontinue study treatment.

The method of recording, evaluating, and assessing causality of AE and SAE and the procedures for completing and transmitting SAE reports are provided in Section 10.6 Appendix 6. Care will be taken not to introduce bias when detecting AEs and/or SAEs. Open-ended and non-leading verbal questioning of the participant is the preferred method to inquire about AE occurrences.

After the initial AE/SAE report, the investigator is required to proactively follow each participant at subsequent visits/contacts. All SAEs will be followed until resolution, stabilization, the event is otherwise explained, or the participant is lost to follow-up (as defined in Section 7.3). For product complaints, the investigator is responsible for ensuring that follow-up includes any supplemental investigations as indicated to elucidate the nature and/or causality. Further information on follow-up procedures is provided in Section 10.6 Appendix 6.

Timing and Mechanism for Collecting Events

Although all AEs after signing the ICF are recorded by the site in the CRF/electronic data entry, SAE reporting to the Sponsor begins after the patient has signed the ICF and has received study drug. However, if an SAE occurs after signing the ICF, but prior to receiving imlunestrant, it needs to be reported ONLY if it is considered reasonably possibly related to study procedures.

Medical occurrences that begin before the start of study intervention but after obtaining informed consent will be recorded on the AE CRF.

All SAEs will be recorded and reported to the Sponsor or designee immediately and under no circumstance should this exceed 24 hours. The investigator will submit any updated SAE data to the Sponsor within 24 hours of it being available. SAEs, including death, caused by disease progression should not be reported unless the investigator deems them to be possibly related to study treatment.

Investigators are not obligated to actively seek AE or SAE after conclusion of the study participation. However, if the investigator learns of any SAE, including a death, at any time after a patient has been discharged from the study, and he or she considers the event to be reasonably related to the study intervention or study participation, the investigator must promptly notify the Sponsor.

Care will be taken not to introduce bias when detecting AEs and/or SAEs. Open-ended and nonleading verbal questioning of the patient and/or legal guardian is the preferred method to inquire about AE occurrences.

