Adverse Event Collection/ CTCAE Grading		Х	Х		Х	Х	Х	Х	Section 8.3	 Collect continuously at every visit and throughout the study CTCAE Version 5.0 For long-term follow-up: all SAEs regardless of relationship to study treatment and adverse events possibly related to study treatment will be collected All adverse events possibly related to study drugs or protocol procedures should be followed until they resolve, are no longer considered to be possibly related, become stable or return to baseline, the patient starts a new therapy, the patient expires, or the patient becomes lost to follow-up. The frequency of evaluation is determined according to the judgment of the investigator
Concomitant Medications		Х	x		Х	х	Х		Section 6.5	 At baseline, record prior and concurrent medications Record all pre-medications, supportive care, and concomitant medication continuously at every visit and throughout study
Lab/Diagnostic Tests	Coagulation	Х							Section 10.4 Appendix 4	 Perform at baseline and as clinically indicated Local testing

	Study Period	Baseline	Stu	Study Treatment (Cycle =28 day				ontinuation ow-Up		
	Cycle	Screening	1 a	nd 2	3	4 and Beyond (if Applicable)	Short-Term Follow-Up ^a	Long-Term Follow-Up ^a		
	Visit	0	1,3	2, 4	5	6 and Beyond (if Applicable)	801	802–8XX		
	Relative Day within a Cycle	≤28	Day 1	Day 15° (± 3)	Day 1 (± 3)	Day 1 (± 3)	Day 30 (± 7)	(± 14)		
Procedure Category	Procedure								Protocol Reference	Instructions
	Hematology	Х	Х	х	X	X	Х		Section 10.4 Appendix 4	 Assessments may be performed up to 3 days prior to Day 1 of each cycle Local testing Cycles 1 and 2 Day 15 hematology required for Arms A, C only
	Clinical chemistry	Х	х	x	Х	х	Х		Section 10.4 Appendix 4	 Assessments may be performed up to 3 days prior to Day 1 of each cycle Central testing Cycles 1 and 2 Day 15 clinical chemistry required for Arms A, C only
	FSH and estradiol levels	x				х	Х		See Section 5.1 and Section 10.4	 For Screening: local FSH/E2 testing for women <60 years when needed to confirm post-menopausal status For On study: local estradiol every 3 cycles, starting on Day 1 of Cycle 4 and again at STFU visit, for women whose postmenopausal status is due to GnRH agonist treatment
	Pregnancy test	Х					Х		Section 10.7 Appendix 7	 Local testing For Screening: serum pregnancy test required for women of child-bearing potential For on Study: per local regulations and/or institutional guidelines For Short-Term Follow-Up: local testing for women of child bearing potential

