10.6.4. Recording and Follow-Up of AE and/or SAE and Product Complaints

AE, SAE, and Product Complaint Recording

- When an AE/SAE/product complaint occurs, it is the responsibility of the investigator to review all documentation (for example, hospital progress notes, laboratory reports, and diagnostics reports) related to the event.
- The investigator will then record all relevant AE/SAE/product complaint information in the participant's medical records, in accordance with the investigator's normal clinical practice. AE/SAE information is reported on the appropriate CRF page and product complaint information is reported on the Product Complaint Form.

Note: an event may meet the definition of both a product complaint and an AE/SAE. In such cases, it should be reported as both a product complaint and as an AE/SAE.

- It is **not** acceptable for the investigator to send photocopies of the participant's medical records to Sponsor or designee in lieu of completion of the CRF page for AE/SAE and the Product Complaint Form for product complaints.
- There may be instances when copies of medical records for certain cases are requested by Sponsor or designee. In this case, all participant identifiers, with the exception of the participant number, will be redacted on the copies of the medical records before submission to Sponsor or designee.
- The investigator will attempt to establish a diagnosis of the event based on signs, symptoms, and/or other clinical information. Whenever possible, the diagnosis (not the individual signs/symptoms) will be documented as the AE/SAE.

Assessment of Intensity

The investigator will use CTCAE version 5.0 (NCI 2018) to assign AE severity grades.

Assessment of Causality

- The investigator is obligated to assess the relationship between study intervention and each occurrence of each AE/SAE.
- A "reasonable possibility" of a relationship conveys that there are facts, evidence, and/or arguments to suggest a causal relationship, rather than a relationship cannot be ruled out.
- The investigator will use clinical judgment to determine the relationship.
- Alternative causes, such as underlying disease(s), concomitant therapy, and other risk factors, as well as the temporal relationship of the event to study intervention administration, will be considered and investigated.
- The investigator will also consult the IB and/or Product Information, for marketed products, in his or her assessment.

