	A medicinal product used for the needs of a clinical trial as described in the protocol, but not as an investigational medicinal product. Examples include rescue medication, challenge agents, agents to assess endpoints in the clinical trial, or background treatment.
NRS	numeric rating scale
OS	overall survival
participant	Equivalent to CDISC term "subject": an individual who participates in a clinical trial, either as recipient of an investigational medicinal product or as a control
P-gp	P-glycoprotein 1

PET	positron emission tomography
PI3K	phosphoinositide 3-kinase
PK/PD	pharmacokinetics/pharmacodynamics
P-gp	p-glycoprotein
PGR	progesterone receptor
PFS	progression-free survival
РО	orally
PR	partial response
PRO/ePRO	Patient-reported outcomes/electronic patient-reported outcomes
PS	performance status
РТ	prothrombin time
QD	once daily
SAC	statistical analysis center
SAE	serious adverse event
SAP	statistical analysis plan
SAR	serious adverse reaction
Screen	The act of determining if an individual meets minimum requirements to become part of a pool of potential candidates for participation in a clinical study.
SD	stable disease
SERD	selective estrogen receptor degrader
SoA	Schedule of Activities
SOC	standard of care
STFU	short-term follow-up
SMD	Senior Management Designee
SRE	skeletal-related event

SUSARs	suspected unexpected serious adverse reactions	
	Refers to an adverse event that occurs in a clinical trial participant, which is assessed by the sponsor and or study investigator as being unexpected, serious, and as having a reasonable possibility of a causal relationship with the study intervention.	
TBL	total bilirubin	
TEAE	Treatment-emergent adverse event: an untoward medical occurrence that emerges during a defined treatment period, having been absent pretreatment, or worsens relative to the pretreatment state, and does not necessarily have to have a causal relationship with this treatment.	
TTC	time to chemotherapy	
UGT1A1	UDP Glucuronosyltransferase Family 1 Member A1	
ULN	upper limit of normal	
WOCBP	woman of childbearing potential	

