The Medical Dictionary for Regulatory Activities (MedDRA) Preferred Term (PT) derived from the verbatim term will be used when reporting AEs by MedDRA terms. The MedDRA Lower Level Term will be used in the treatment-emergent computation. Severity grades will be assigned by the investigator using National Cancer Institute - Common Terminology Criteria for Adverse Events (NCI-CTCAE) version 5.0. Preexisting conditions are defined as AEs that either are ongoing at informed consent and or end on or after informed consent. Pre-existing conditions will be included in the listing of AE so that the history of AEs can be traced.

Treatment-emergent adverse events (TEAEs) are events that first occurred or worsened in severity after baseline. Treatment-emergent adverse events will be summarized by System Organ Class (SOC) and by decreasing frequency of PT within SOC.

Adverse event analyses will include summaries of the following:

- Overview of adverse events
- TEAEs, including severity (any grade and grade ≥3) and possible relationship to study drug
- Cumulative TEAE incidence at 3 months, 6 months, and 1 year, will be provided in accordance with the draft EMA guideline (EMA 2017) on evaluation of anticancer medical products in humans if deemed appropriate. In case where the time on therapy is longer, additional time points up to approximately 5 years may also be considered.
- Serious adverse events, including possible relationship to study drug
- Adverse events leading to dose adjustments/omissions
- Discontinuations from study treatment due to AEs or death
- Time to onset for selected TEAEs
- Adverse events of special interest (AESI): Categories of AESI may be modified as the understanding of the safety of imlunestrant increases. The final list of categories will be maintained at both compound and study level and reported in the CSR.
- **Consolidated AEs** are composite AE terms consisting of synonymous PTs to allow meaningful interpretation of the AE data. The final list of consolidated AE categories and PTs will be maintained at both compound and study level and reported in the CSR.

Deaths

- Deaths (all deaths and deaths within 30 days of treatment discontinuation) and their primary cause (study disease progression, AE, other)
- Adverse events leading to death

Laboratory Abnormalities

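### Protocol Section 8.3 and Appendix 6 define a reasonable possibility of causality differently, so the investigator's yes/no relatedness call has two thresholds

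*Protocol*

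**What the plan says.** Protocol Section 8.3 asks the investigator to document "whether or not an AE has a reasonable possibility of being related to study treatment, study device, or a study procedure", weighing the disease, concomitant treatment and other pathology. It then defines the key term: a reasonable possibility "means that there is a cause and effect relationship between the investigational product, study device, and/or study procedure and the AE". The next sentence sets the response format: "The investigator answers yes/no when making this assessment".

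Later in Section 8.3 the reader is told that "The method of recording, evaluating, and assessing causality of AE and SAE" is provided in Appendix 6. There, under the heading on causality in Section 10.6.4, a reasonable possibility "conveys that there are facts, evidence, and/or arguments to suggest a causal relationship, rather than a relationship cannot be ruled out".

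Other places use the term or a close relative without defining it:

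- The SUSAR entry in Appendix 16 covers events assessed "as having a reasonable possibility of a causal relationship with the study intervention".
- For long-term follow-up, the Schedule of Activities (Section 1.3) says that, besides all SAEs, "adverse events possibly related to study treatment will be collected".
- The SAP's safety analyses (Section 4.4.2) list "Serious adverse events, including possible relationship to study drug", and Protocol Section 9.4.5 plans matching summaries.

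**The concern.** A binary causality question needs one threshold. Here the same term carries two. The stricter one stands directly in front of the yes/no instruction, where site staff are most likely to read it.

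The Section 8.3 sentence also contradicts its own context, because it turns a possibility into a fact. An investigator who follows it to the letter would answer no for any event where the evidence suggests a drug effect without establishing it. Those are the events that Appendix 6 means to capture.

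At stake is the consistency of relatedness coding between sites, and with it the meaning of the related-event summaries. Some reporting steps also turn on relatedness. Safety is a secondary objective of an open-label trial of an agent not yet authorised in the EU, so these summaries will be read closely.

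**Working it through.** There is no sample size, power or alpha figure to reproduce. The check sets the two definitions side by side and then traces where the answer is used.

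**Step 1. Apply both definitions to the three possible states of evidence.**

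| Evidence for causality | Section 8.3, read literally | Appendix 6 |
|---|---|---|
| Causation established | yes | yes |
| Causation suggested, not established | no | yes |
| Causation merely not excluded | no | no |

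The texts agree in the first and third rows and conflict in the second.

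**Step 2. Ask whether one text overrides the other.** Section 8.3 refers to Appendix 6 for the method of assessing causality. It does not say that the appendix replaces the definition just given, and Appendix 6 makes no such claim either. Both stand in the current body of the protocol, not in the amendment history.

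**Step 3. Trace the use of the answer.**

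- *Summaries.* AEs and SAEs are tabulated by possible relationship to study drug (Protocol Section 9.4.5; SAP Section 4.4.2).
- *Regulatory reporting.* Section 10.6.4 names the causality assessment among the criteria for reporting obligations. The SUSAR definition uses the disputed term.
- *SAEs before dosing.* Under Section 8.3 these are reported only if thought related to study procedures.
- *SAEs caused by progression, including deaths.* Under Section 8.3 these are not reported unless thought possibly related to treatment. Section 8.3.4 has a similar rule for deaths from the study disease.
- *SAEs learned of after discharge from the study.* Under Section 8.3 the investigator must notify the sponsor if the event is considered reasonably related.
- *Non-serious AEs in long-term follow-up.* Under Section 1.3 these are collected only if possibly related.

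The last four use near-variants of the term. The only definitions a site has to interpret them are the two that conflict.

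**Step 4. Separate what does not inherit the conflict.** The dose-adjustment sections for imlunestrant (6.6.1) and abemaciclib (6.6.3) explain relatedness in their own words, as a *reasonable causal relationship* with the drug. They cite neither definition. This is a third, unexplained wording, not a use of the first two.

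**Step 5. Size.** The documents give neither the incidence of AEs by evidence category nor any information on which text sites follow. The number of events in the second row of the table cannot be derived.

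**The case against.** The strongest reply is that this is loose drafting with little practical effect. Section 8.3 points to Appendix 6 for causality, speaks elsewhere of potential relatedness, and would make no sense if a possibility had to be a certainty. Experienced investigators may well apply the Appendix 6 standard anyway. This shows which meaning was probably intended. It does not remove the contrary definition from the place where the question is asked.

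Several safeguards also limit the consequences, and they stand:

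- SAEs in general must reach the sponsor within 24 hours; relatedness is not the general gate.
- In long-term follow-up, all SAEs are collected whatever the attribution.
- SUSAR status may rest on the sponsor's assessment as well as the investigator's.
- Aggregate safety data are reviewed at least quarterly, and unblinded SAE comparisons are possible (Section 8.2.3).
- TEAEs are also summarised without regard to relatedness.
- Investigators may revise a causality opinion.

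These safeguards do not help where an event is never sent because the site judged it unrelated.

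A reader might infer more than the documents support:

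- *That expedited reports will be missed widely.* The safeguards above argue against that. The exposure is confined to the relatedness-dependent reports in Step 3.
- *That imlunestrant in Arm A will attract fewer related calls than the marketed drugs.* Nothing in the documents shows this. Section 2.1 already describes Phase 1 events considered possibly related to imlunestrant, and Section 10.6.4 sends investigators to the Investigator's Brochure or product information.
- *That the conflict governs the dose tables.* They use separate wording, and Section 6.6.3 lets investigators suspend or reduce abemaciclib without meeting a listed criterion.
- *That a percentage change in related-AE rates can be stated.* Any such figure would only restate assumed shares.

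**Conclusion.** The inconsistency is real and should be corrected. One term in the current protocol has two definitions, and they give opposite answers for events with suggestive but unproven causality. The Section 8.3 sentence is wrong as written.

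The effect is limited to relatedness coding, the descriptive summaries and regulatory decisions that draw on it, and the few reports that depend on it. Its size is unknown and cannot be estimated from the documents. PFS, OS and every alpha-controlled test are unaffected.

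The conclusion assumes that at least some sites may read Section 8.3 literally. The documents do not show whether any has done so.

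**What to change.** Replace the defining sentence in Section 8.3 with the Appendix 6 definition, or with a cross-reference to it, and carry that one definition into the CRF guidance. Make clear that the related and possibly related wording in the collection and reporting rules refers to it.

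Reconcile the separate wording in Sections 6.6.1 and 6.6.3 with that definition. This review proposes no dose rule and takes no position on which clinical rule is right.

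Tell all sites in a neutral clarification. Do not re-query only the SAEs already coded as unrelated: that could move calls in one direction only, in an open-label trial, with no evidence that any site used the strict reading.

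The cost is one sentence in the next amendment or a clarification letter, the alignment of the related wording, and one site communication. No analysis, event count or boundary changes.
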